CLINICAL STUDY PROTOCOL

The effect of methenamine hippurate to reduce antibiotic prescribing due to new episodes of urinary tract infections (UTI) in elderly women with recurrent UTI – a triple-blinded, randomized placebo-controlled phase IV study

Study Code: ImpresU WP3 (Improving rational prescribing for UTI in frail elderly Work Package 3)

EudraCT Number: 2018-002235-15

Version Number: Version 11.1

Date: 7th July 2021

Sponsor: University of Oslo

Principal investigator(s): [name]

SYNOPSIS

Title: The effect of methenamine hippurate to reduce antibiotic prescribing due to new episodes of urinary tract infections (UTI) in elderly women with recurrent UTI – a triple-blinded, randomized placebo-controlled phase IV study

EudraCT Number: 2018-002235-15

Indication: Recurrent UTI in elderly women is a major driver of antibiotic prescription.

Rational for conducting the study: There is a need for a large well-conducted randomised controlled trial (RCT) to clarify both the safety and preventive effect of methenamine hippurate for longer term use.

Primary objective: The primary objective of this study is to investigate if taking methenamine hippurate reduce the need for antibiotic usage due to recurrent UTI (measured as the number of courses of antibiotics).

Secondary objectives:

- to investigate if methenamine hippurate will have a prolonged effect on antibiotic usage even after discontinuation
- to investigate if taking methenamine hippurate reduces the incidence of UTI
- to investigate if methenamine hippurate can reduce severity of UTI symptoms
- to investigate if methenamine hippurate can reduce duration of UTI episodes
- to investigate if number of complications such as pyelonephritis and hospital admission for UTI differ between methenamine hippurate and placebo
- To investigate if phylogenetic subgroups of E. Coli found at inclusion is an effect modifier in the above outcomes.

Study design: Blinded randomised controlled phase IV trial where patients are randomised to active intervention (methenamine hippurate) or controls (placebo).

Study population: Women aged ≥ 70 years with recurrent UTIs in community dwellings.

Number of patients: 400.

Inclusion criteria:

- woman
- age ≥ 70 years
- recurrent UTIs defined as ≥ 3 episodes of antibiotic treated acute cystitis (acute symptoms specific/related to the urinary tract) during the last twelve months or ≥ 2 episodes during the last 6 months
- able and willing to comply with all trial requirements
- able and willing to give informed consent

Exclusion criteria:

- the patient has taken methenamine hippurate within the last 12 months
- the patient is allergic to methenamine hippurate
- the patient is having current antibiotic prophylaxis for UTI
- the patient has a urinary catheter (chronic indwelling catheters as well as intermittent urinary catheterisation)
- the patient has known severe chronic renal failure or estimated creatinine glomerular filtration rate ≤ 30 ml/min (known = registered in GP clinical records)
- the patient has a known condition or treatment associated with significant impaired immunity (e.g. long-term oral steroids, chemotherapy, or immune disorder) (known = registered in GP clinical records)
- the patient has a known severe hepatic impairment (known = registered in GP clinical records)
- the patient is suffering from severe dehydration
- the patient has gout
- the patient has a need for long term use of antacids such as magnesium hydroxide, magnesium carbonate, aluminium hydroxide
- the patient has a life expectancy estimated by a clinician to be less than six months
- the patient has been involved in, including completion of, follow-up procedures, in another clinical trial of an investigational medicinal product in the last 90 days
- the patient suffers from incontinence too severe to be able to provide a voided urine specimen
- the patient is participating in ImpresU Work Package 2
- the patient is suffering from significant known abnormal renal tract anatomy/physiology (i.e. single kidney, persistent urinary tract stone disease, severe vesicoureteral reflux) or neuropathic bladder disorders
- lactose intolerance.

Premature termination of the study

The difference between groups in SAEs deemed to be linked to possible treatment with methenamine hippurate will be continuously monitored without breaking the code. The study will be terminated in case there are significantly more SAEs within one of the groups during the trial.

Investigational product, dosage and administration: Methenamine hippurate 1 gram or placebo per os morning and evening day 1-180.

[figure not shown]
Primary outcome variables and examinations: Number of UTI courses during day 2-180

Study period: 1 November 2019 to 31 December 2022.

SIGNATURE PAGE

LIST OF APPENDICES

1. Farmasøytisk/kjemisk dokumentasjon for Hiprex, Kragerø tabletproduksjon A/S.
2. SmPC Hiprex, Meda.
3. Etikettforslag norsk
4. Patient reported outcome
5. Safety reporting flow-chart
6. EMA-akkreditering
7. Mail Legemiddelansvarsforsikring
8. Legemiddelansv.forsikring Kragerø tabl.prod.

LIST OF ABBREVIATIONS

Abbreviation	Explanation
ADR	Adverse Drug Reaction
AE	Adverse Event
AMR	Antimicrobial Resistance
CA	Competent Authority
EC	Ethics Committee
(e)CRF	(electronic) Case Report Form
EDC	Electronic Data Capture
GCP	Good Clinical Practice
GP	General Practitioner
ICF	Informed Consent Form
IMP	Investigational Medicinal Product
ImpresU	Improving rational prescribing for UTI in frail elderly
ISF	Investigator Study File
OOH	Out Of Hours Service
PI	Principal Investigator
PRO	Patient Reported Outcome (PRO)
RCT	Randomised Controlled Trial
RO	Research Online
SAE	Serious Adverse Event
SAR	Serious Adverse drug Reaction
SmPC	Summary of Product Characteristics
SUSAR	Suspected Unexpected Serious Adverse Reactions
UTI	Urinary Tract Infection
WP	Work Package

1. INTRODUCTION

1.1. Background

Recurrent urinary tract infection (UTI) in elderly women is a major driver of antibiotic prescription (1-9). Hence, the question of feasible and appropriate preventive measures are important issues in this field. Methenamine hippurate is frequently prescribed in Norway and Sweden as prophylaxis for recurrent UTI (9). Methenamine hippurate is hardly used outside of Scandinavia. Methenamine hippurate acts via the production of formaldehyde from hexamine, which in turn acts as a bacteriostatic agent, therefore methenamine hippurate is not defined as an antibiotic. According to a Cochrane review 2012 the rates of adverse events for preventing UTI was low (10). Although this review showed methenamine hippurate might be effective in preventing UTI in the short term, there is a need for large well-conducted randomised controlled trial (RCT) to clarify both the safety and effectiveness of preventive methenamine hippurate for longer term use (11-16). This is particularly important for longer term use for people without neuropathic bladder disorders (10). A Norwegian longitudinal observational study including women aged 50-80 years with recurrent UTI indicated a significant and large reduction of more than 50% in antibiotic prescriptions for UTI after start of prophylactic methenamine hippurate ([name], personal communication). This further strengthens the need for an RCT of methenamine hippurate as prophylaxis for recurrent UTI.

Escherichia coli (E. coli) is a part of the human gastrointestinal microbiota (17). Uropathogenic E.coli from fecal reservoirs are the predominant causative microbes in uncomplicated UTIs (18-20). Previous studies have shown that strains of E.coli can be divided into phylogenetic subgroups (A, B1, B2, C, D, E and F), and that subgroup B2 and D represents the most virulent types and are associated with extra-intestinal infections (21-23).

We aim to investigate whether the phylogenetic subgroups of E.coli present in the urine cultures at inclusion can have a modifying role on the preventive effect of Methenamine hippurate in this study. If feasible, we will also investigate whether or not subsequent episodes of acute UTIs in elderly women with recurrent UTI are caused by E.coli of the same phylotype.

1.2. Rationale for conducting this study

Existing knowledge suggests that methenamine hippurate is a safe drug with few and mild side effects and with the potential to significantly reduce antibiotic usage for women with recurrent UTIs. Methenamine hippurate has been on the market for a long time but has never been tested to prevent recurrent UTIs in larger RCTs with long time follow-up. Hence, this must be proven in a large randomised trial before recommending large scale use of this drug (10).

1.3. Risk/Benefit evaluation

Potential benefits from IMP:

- decreased total use of UTI antibiotics
- reduced antibiotic pressure on gut microbiota in the population and possibly reduced antimicrobial resistance (AMR) in the population
- decreased number of UTIs
- increased quality of life.

Potential risks from IMP:

- polypharmacy, many patients have a large number of regular medication, and methenamine hippurate will be a new one for six months
- simultaneous intake of sulphonamide antibiotics can increase risk of crystalluria. Therefore methenamine hippurate will temporarily be paused if the participant gets a course of sulphonamide antibiotics. There are no other known clinical relevant interactions between methenamine hippurate and other pharmaceuticals.

Anticipated adverse drug reactions in the study:

Methenamine hippurate is well tolerated and adverse effects are rare and generally mild (10). Possible side effects might be minor gastrointestinal upsets, dysuria (seldom), abdominal cramps, anorexia, rash and stomatitis (10). The trial team will be available on telephone for urgent cases during the whole study period. This will be solved for each country.

Risk/benefit rationale:

- The benefit of the study is potentially great for elderly women with recurrent UTI resulting in fewer UTI episodes, reduced antibiotic usage and therefore also reducing the risk of AMR.
- The risk of the study is considered to be very small.

In summary the benefits greatly outweigh the potential small risks. This will be evaluated and confirmed by relevant ECs before commencing the trial.

2. STUDY OBJECTIVES AND ENDPOINTS

The primary objective of this study is to investigate if taking methenamine hippurate reduce the need for antibiotic usage due to recurrent UTI (measured as number of antibiotic courses). The remaining objectives are considered secondary. Pyelonephritis, hospitalization and death will be registered as safety endpoints in the study.

Objectives	Outcome Measures / variables / endpoints	Time point(s) of evaluation of this outcome measure (if applicable)
Primary Objective		
1 The primary objective of this study is to investigate if taking methenamine hippurate reduces the need for antibiotic usage due to recurrent UTI (measured as number of antibiotic courses).	Number of UTI antibiotic treatments during the six months of treatment. If the participant receives >1 antibiotic course for UTI without symptom relief it is regarded as one episode and counted as one antibiotic treatment. If there has been an asymptomatic period of at least 14 days in-between two UTI antibiotic	After six months of treatment.

		courses, this is regarded as a new antibiotic treatment.	
Secondary Objectives			
2a	To investigate if methenamine hippurate will have a prolonged effect on antibiotic usage even after discontinuation.	Number of UTI antibiotic treatments during the six months following completion of treatment. If the participant receives >1 antibiotic course for UTI without symptom relief it is regarded as one episode and counted as one antibiotic treatment. If there has been an asymptomatic period of at least 14 days in-between two UTI antibiotic courses, this is regarded as a new antibiotic treatment.	Six months after completing (12 months after commencing) treatment.
2b	To investigate if taking methenamine hippurate reduces the incidence of UTI.	Number of UTIs (acute symptoms specific/related to the urinary tract) during the six months of treatment. If the participant has had >1 UTI episode without symptom relief it is regarded as one episode. If there has been an asymptomatic period of at least 14 days in-between two UTI episodes, this is regarded as a new episode.	After six months of treatment.
2c	To investigate if methenamine hippurate can reduce severity of UTI symptoms.	Registration of symptom severity when initiating treatment for UTI.	After six months of treatment.
2d	To investigate if methenamine hippurate can reduce duration of UTI episodes.	Registration of number of days of symptoms during UTI episodes.	After six months of treatment.
2e	To investigate if number of complications such as pyelonephritis and hospital admission for UTI differ between methenamine hippurate and placebo.	Registration of number of pyelonephritis and hospital admission for UTI.	Six and 12 months after commencing treatment.
2f	To investigate if phylogenetic subgroups of E. coli found at inclusion is an effect modifier in the above outcomes.	(see above)	(see above)

[figure not shown]
3. STUDY DESIGN AND PROCEDURES

3.1. Overall study design and flow chart

Study design: Blinded randomised controlled phase IV trial where patients are randomised to active intervention (methenamine hippurate) or controls (placebo).

Setting and study population: Women aged ≥ 70 years with recurrent UTIs in primary care. A total of 400 patients will be randomized in this trial, with approximately 100 patients in each of the participating countries; Norway, Sweden, Poland and the Netherlands.

Diagram 1. Schematic diagram of procedures:

3.2. Rationale for study design

This is a triple blinded RCT in women aged ≥ 70 years with recurrent UTIs, defined as ≥ 3 episodes of antibiotic treated acute cystitis (acute symptoms specific/related to the urinary tract) during the last twelve months or ≥ 2 episodes during the last six months.

The trial will be triple blinded in order to avoid bias by the patient, the doctor or the person doing statistical analysis. As methenamine hippurate is a prophylactic treatment six months of therapy is necessary. To be able to evaluate if there is a prolonged effect of treatment another six months follow-up is necessary.

The effect of methenamine hippurate is dependent on acidic urine. The hippurate component work as acidifying the urine in patients. We will register urine pH for all patients in the study and see if this has a modifying effect on the results. We will not use lack of acidic urine as an exclusion criterion.

Potential effect modifiers to be registered in CRF and adjusted for in the analysis:

- patient's age
- urine acidity (pH)
- number of antibiotic courses for UTIs in the 12 months preceding inclusion in the study
- presence of urease/stone-producing bacteria in urine culture day 1 such as *proteus*, some *klebsiella* species, *Morganella morganii*, *Corynebacterium urealyticum* and *providencia*
- use of local oestrogen
- patient has diabetes mellitus
- obesity defines as BMI ≥ 30
- presence of known abnormality of the urogenital tract
- if the patient is sexually active
- if the patient previously have experienced kidney stone.

3.3. Table 1. Study visits

Day(s)	Visit 1 Screening and randomisation	Telephone follow-up in case of acute UTI episode(s)	Telephone follow-up every 30 days in all patients	Telephone contact by end of treatment	Telephone contact by end of study
	1	2-360	2-180	180	360
Informed consent	X				
Demography, level of care	X				
Medical history	X				
Physical examination***	X				
Dipstick urinalysis and urine culture	X	X			
Inclusion/exclusion criteria	X				
Randomisation	X				
Patient Reported Outcome		X	X	X	X
Concomitant medication**	X				
Serious Adverse Events		X	X	X	X*

* In case of SAE present and not resolved by day 360, this will be followed until resolution.

** After visit 1 concomitant medication will only be registered in case of SAE, otherwise not.

*** If needed to determine eligibility or complete baseline data.

3.4. Study assessments

Visit 1 – Screening, inclusion and randomisation

Visit 1 (screening and inclusion) is performed by a trial team member or specially trained local investigators at primary health care centres. Before screening, the Investigator will provide thorough oral and written information about the study to the subject. The subject will be given the

opportunity to ask questions and be given sufficient time to consider participation. Subject who agree to participate will give signed and dated informed consent prior to any study-related activity. The investigator will keep a subject screening log and a subject enrolment log.

The patients will when possible be found through a screening procedure of each GPs (General Practitioners) Electronic Patient Record, finding patients who had at least 3 courses of UTI antibiotics last year. Otherwise eligible patients will be identified through doctors and nurses in clinical work with frail elderly. Only patients fulfilling the inclusion criteria and consenting to participate will be included. Demography and level of care will be registered. Medical history including current medication, risk factors for recurrent UTI such as urinary bladder dysfunction (e.g. overactive bladder), diabetes mellitus, obesity (BMI >30), local treatment with oestrogen, sexual activity or abnormality of the urogenital tract. A voided urine specimen will be collected and dipstick urinalysis regarding pH, nitrite and leukocyte esterase will be performed as well as a urine culture, also asking for ureas-producing bacteria. In case of growth of pure cultures of *E. coli* in the inclusion urine culture, we will freeze the isolates of *E. coli* and send them to the department of clinical microbiology at Sahlgrenska University Hospital in Sweden for analysis of phylogenetic subgroups according to published protocols using PCR-technique.

If the patient presents with symptoms of an acute UTI or are on antibiotic treatment for a UTI at the inclusion visit, the infection is handled by regular health services (GP or out of Hours (OOH) service). The patient will wait until 2 weeks after finishing treatment for the UTI before the researcher completes the inclusion and takes the baseline urine sample. The treatment with IMP will start the day after the completed inclusion of the patient. The current UTI should be registered at the baseline form as a UTI prior to inclusion in the study. The same procedure will be followed if the patient is on prophylactic treatment with UTI antibiotics, but is willing to stop the prophylactic treatment to enter the study. A note of the actions taken will be written in the comments section in the baseline CRF by the responsible researcher.

All data related to inclusion visit including trial name, study-ID and informed consent will be documented in the medical record of the patient.

Telephone follow-up in case of acute UTI episode(s)

Any episodes of acute UTI during the follow-up period (day 2-360) will be handled by regular health services (GP or out of Hours (OOH) service). Participants are informed at inclusion (Visit 1) to contact the trial team in case of any UTI-related health care contacts during the follow-up period. The study team will follow up each UTI episode until resolved with registration of relevant data by telephone contact and by ordering copies of medical records regarding the UTI episode including laboratory results regarding urinary dipsticks and urine culture.

Following data will be collected in case of acute UTI episode(s) during day 2-360 (telephone follow-up and from medical record):

- confirmation and registration of UTI symptoms (acute symptoms specific/related to the urinary tract), registration of symptom severity when initiating treatment for UTI. This will be measured by a scale 0-6 (no symptoms to worst possible) for each of the three cardinal

symptoms and general condition, Patient Reported Outcome (PRO) – grading of symptoms, see appendix

- UTI antibiotic treatment (name of drug, dosage and duration)
- registration of any pyelonephritis and hospital admission for UTI
- ordering copies of medical records regarding the UTI episode including laboratory tests performed by regular health service (dipstick urinalysis regarding nitrite and leukocyte esterase and urine culture)
- SAEs, whereas relationship with IMP cannot be excluded.

In case of an episode of UTI all clinically relevant data have already been recorded in the patient's medical record by the physician, therefore these telephone follow-ups will only be recorded in the CRF. In case of SAE this will be recorded in the medical record.

Telephone contacts every 30 days during the first six months as well as day 360

During telephone contacts every 30 days during the first six months as well as day 360 registration of any symptoms and side effects from the trial medication will be recorded as well as SAEs, whereas relationship with IMP cannot be excluded. Participants will be asked if they have forgotten to contact the study team in case of any UTI-related health care contacts. If so, the study team will follow up these UTI episode(s) with registration of relevant data as described above.

In case of new UTI not recorded, we will record PRO using the scale. In case of an episode of UTI all clinically relevant data have already been recorded in the patient's medical record by the physician, therefore these telephone follow-ups will only be recorded in the CRF. In case of SAE this will be recorded in the medical record. By the end of the project period, the study team will contact the patients' GP, and ask the GP to go through the patients' records during the project period in order to validate the number of UTI episodes.

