2. STUDY OBJECTIVES AND ENDPOINTS

The primary objective of this study is to investigate if taking methenamine hippurate reduce the need for antibiotic usage due to recurrent UTI (measured as number of antibiotic courses). The remaining objectives are considered secondary. Pyelonephritis, hospitalization and death will be registered as safety endpoints in the study.

Objectives		Outcome Measures / variables / endpoints	Time point(s) of evaluation of this outcome measure (if applicable)
Primary Objective			
1	The primary objective of this study is to investigate if taking methenamine hippurate reduces the need for antibiotic usage due to recurrent UTI (measured as number of antibiotic courses).	Number of UTI antibiotic treatments during the six months of treatment. If the participant receives >1 antibiotic course for UTI without symptom relief it is regarded as one episode and counted as one antibiotic treatment. If there has been an asymptomatic period of at least 14 days in-between two UTI antibiotic courses, this is regarded as a new antibiotic treatment.	After six months of treatment.
Secondary Objectives			
2a	To investigate if methenamine hippurate will have a prolonged effect on antibiotic usage even after discontinuation.	Number of UTI antibiotic treatments during the six months following completion of treatment. If the participant receives >1 antibiotic course for UTI without symptom relief it is regarded as one episode and counted as one antibiotic treatment. If there has been an asymptomatic period of at least 14 days in-between two UTI antibiotic courses, this is regarded as a new antibiotic treatment.	Six months after completing (12 months after commencing) treatment.
2b	To investigate if taking methenamine hippurate reduces the incidence of UTI.	Number of UTIs (acute symptoms specific/related to the urinary tract) during the six months of treatment. If the participant has had >1 UTI episode without symptom relief it is regarded as one episode. If there has been an asymptomatic period of at least 14 days in-between two UTI episodes, this is regarded as a new episode.	After six months of treatment.
2c	To investigate if methenamine hippurate can reduce severity of UTI symptoms.	Registration of symptom severity when initiating treatment for UTI.	After six months of treatment.

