5.1.1. Intention to treat analysis and missing data

The primary statistical analysis is intention to treat including all patients randomized contributing with a full set of baseline observations. A sensitivity analysis will be done also including patients randomized with incomplete baseline observations where we may have to omit one or a few baseline covariates from the regression analyses.

Patients leaving the study completing at least three but less than six of the first six months will contribute with data up until they leave the study and this data will be extrapolated as if it was six months.. If they remained for less than three months their observations will be imputed with the mean from similar patients. Similar patients are defined as having an age of \pm five years and belonging to the same intervention group. Patients leaving during the second six months period will also contribute with data as described above.

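### The project-end GP record review is used only to validate UTI counts, while women who leave get extrapolated or donor-mean values without first using the dated courses that review could supply

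*Protocol*

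**What the plan says.** Protocol 3.4 sets up two routes by which UTI episodes reach the trial. During follow-up, participants are told "to contact the trial team in case of any UTI-related health care contacts during the follow-up period", and scheduled calls ask about contacts they forgot to report. Separately, "By the end of the project period, the study team will contact the patients' GP", who is asked to check the patients' "records during the project period in order to validate the number of UTI episodes". This second route is not restricted to women who completed follow-up.

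The primary outcome is "Number of UTI antibiotic treatments during the six months of treatment" (SAP 2), with courses merged into one treatment unless at least 14 symptom-free days separate them.

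SAP 5.1.1 deals with women who leave during the first six months. Those who stayed at least three months "will contribute with data up until they leave the study and this data will be extrapolated as if it was six months". For the rest: "If they remained for less than three months their observations will be imputed with the mean from similar patients", where similar means the same arm and an age within five years. Leavers in the second six months are handled the same way. Protocol 8.2 rescales all partial first-period data. Neither section mentions GP records.

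Protocol 4.4.1 lists loss to follow-up as a reason for discontinuing. Women who stop the study drug without withdrawing consent stay in follow-up, so the point concerns those who leave or are lost.

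**The concern.** The protocol itself treats the medical record as a credible source for this outcome. Eligible women are found by searching GP records, "finding patients who had at least 3 courses of UTI antibiotics last year", and for a UTI episode "all clinically relevant data have already been recorded in the patient's medical record by the physician". When a woman can no longer be reached, her own reports and the calls both stop, but the GP review does not depend on her being reachable. As written, the plan still assigns her a constructed count.

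Three things are at stake. A single donor mean is analysed as if it had been observed, which makes the standard error too small. If leaving is related to a woman's UTI rate, women who remained are the wrong donors. Both rules can also produce non-integers (one course in four months becomes 1 × 6/4 = 1.5), although SAP 6 justifies the negative binomial model by the outcome being an integer.

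Nor is there a written rule for what happens to the primary count when the GP review and the episode forms disagree, so that choice could be made after the data are seen.

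**Working it through.** **Inputs.** From Protocol 8.1: means 2.0 and 1.5, SD 1.5, two-sided 0.05, power 0.80, 25% loss. From Protocol 5.1: 200 medication sets per arm. The share leaving before month 3 is not stated and is varied as an assumption.

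**1. The plan's sample size.** Effect size 0.5/1.5 = 0.33. The exact t-test needs 142.25, so 143 per arm (286). Mann-Whitney needs 142.25/(3/π) = 148.96, so 149 per arm (298). Allowing for loss, 298/0.75 = 397.3. The stated 286, 298 and 397 reproduce.

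**2. Standard error under donor means.** Let a fraction f in each arm (n = 200) receive an arm mean; age matching is ignored. The information comes from n(1−f) women, but the software counts n women with variance shrunk by (1−f).

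- True SE = 1.5·√(2/(n(1−f)))
- Reported SE = 1.5·√(2(1−f)/n)
- Ratio = 1−f; actual type I error = 2(1−Φ(1.96(1−f)))

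| f | True SE | Reported SE | Ratio | Actual type I error |
|---|---|---|---|---|
| 5% | 0.154 | 0.146 | 0.95 | 0.063 |
| 10% | 0.158 | 0.142 | 0.90 | 0.078 |
| 12.5% | 0.160 | 0.140 | 0.875 | 0.087 |
| 25% | 0.173 | 0.130 | 0.75 | 0.142 |

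The last row requires all 100 losses to occur before month 3. With complete counts the SE is 1.5·√(2/200) = 0.150.

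**3. Simulation.** This used 4,000 runs per scenario, gamma-Poisson counts, 25% dropout unrelated to outcome, and an unadjusted test on means as a stand-in for the planned model. Type I error was 0.149 if all losses were early, 0.091 if half were, and 0.049 if all came after month 3 at a constant rate. Extrapolation therefore did little harm in that last case; the donor mean drives the error.

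**4. Dropout related to UTI rate (assumed).** If the chance of leaving is proportional to a woman's own rate, the mean among stayers falls by f/(1−f) × σ²/μ, where σ² is the variance of the underlying rates (1.5² minus the mean).

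- Active arm only: (0.25/0.75) × 0.75/1.5 = 0.167, so a true difference of −0.50 becomes about −0.67 (simulated −0.66).
- Control arm only: (0.25/0.75) × 0.25/2.0 = 0.042, giving about −0.46 (simulated −0.46).

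Both figures assume that all losses are early. Real counts would remove this bias for the women recovered.

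**5. Power on the plan's t-test assumptions.** Power = Φ((1/3)·√(n/2) − 1.96).

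- 150 per arm: Φ(0.927) = 0.82
- 175 per arm (half of the losses recovered): Φ(1.158) = 0.88
- 200 per arm (all recovered): Φ(1.373) = 0.92

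**The case against.** - **A correction route already exists.** Episode data are taken from medical records as well as by telephone (Protocol 3.4), requested reports go into the CRF (9.1.1), queries can lead to corrections (9.2), and the monitor checks main endpoints against source (10.1). A reader might infer that the GP review can never change a count; these sections do not support that. What is missing is a rule for this review and its use for women who left.
- **The GP record may not hold the outcome exactly.** The review is worded for episodes, not dated courses. Out-of-hours or hospital treatment may be absent, and the 14-day rule needs symptom dates. Record-only counts for leavers could run low relative to women also followed by telephone, which would bias the comparison if dropout differs by arm. This stands, and it is why a telephone-only sensitivity analysis is needed.
- **Some leavers cannot be recovered.** Women who withdraw consent may not permit further access, Protocol 11.2 and 11.3 describe record access for verification, and a woman who dies has no later count. This stands.
- **The standard-error fault belongs to single imputation.** An offset or multiple imputation would address it without any records. This is correct, so the fix has to change that rule as well.
- **A complete-case analysis is planned (SAP 5.1.2).** It avoids constructed values but is not primary, and it does not recover any data.

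**Conclusion.** The point holds as a recommended change. The trial already intends to request information that could replace constructed primary counts for some leavers, and the SAP does not use it.

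The size is a range because the documents give neither the early-leaver share nor the recoverable share. With 5% to 25% of women on donor means, the reported SE is 0.95 to 0.75 of the true value and actual type I error is about 0.06 to 0.14. Complete-case power of 82% would become about 88% with half the losses recovered and at most 92% with all. All of these figures are normal-theory stand-ins for a covariate-adjusted negative binomial model and indicate size and direction only.

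Stronger readings are tempting but unsupported. A reader might infer that the standard error will be 25% too small; that needs every planned loss to fall before month 3. A reader might expect power to go from 82% to 92%; that needs full recovery, and it starts from a complete-case figure although the primary analysis also keeps leavers' partial data. Nor do the documents show that extrapolation after month 3 is seriously harmful, or that the GP record is a complete account of the outcome.

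**What to change.** 1. Word the GP request to cover dated UTI antibiotic courses as well as episodes, identically in both arms.
2. State in SAP 5.1.1 that, for a woman who left, is alive and whose consent to record access still holds, these courses fill the uncollected part of the six months. Apply the same rule to the second period for objective 2a.
3. Have discrepancies with the episode forms settled under the 14-day rule by staff blind to allocation, before unblinding, with the rule written down in advance.
4. For time that neither source covers, including time after death, use an offset for observed time or multiple imputation in place of the single donor mean.
5. Add a sensitivity analysis on telephone-ascertained data alone, and report by arm how many women had time filled from records.

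The cost is SAP text, a somewhat broader request to GPs and a blinded reconciliation in four countries, built on a review and blinding already planned. The consent wording must be checked first. Protocol 12 lists a change in how the primary variable is measured as an example of a substantial amendment, so the sponsor should decide whether this falls under it. Symptom severity (2c), and probably duration (2d), cannot be recovered this way.
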